Version 23JUL2020 Page 6 of 23

Study Duration	The duration of the study is expected to be approximately 2 years from the date of first enrollment (1 year for enrollment of approximately 100 subjects and a year for follow-up of 60 accrued subjects).		
Participant Duration	It will take 12 month for each individual participant to complete all participant visits.		
Population	The patients with obstructive superficial femoral or popliteal arteries disease as the main reason for their symptoms will be enrolled in this study.		
Study Sites	NYU Langone Health		
Number of participants	Number of participants projected for the entire study 100		
Description of Study Procedure	All subjects will undergo percutaneous revascularization of the femoro-popliteal arteries using a DAS or OAS device and balloon angioplasty as per the randomization arm. All patients will undergo at least 3 runs of IVUS: • a pre-treatment run to assess the severity and morphology of the plaque composition • a post-atherectomy run to assess changes post atherectomy treatment • a post drug coated balloon angioplasty (followed atherectomy) to assess changes in overall volumes.		
Statistical Analysis	The sample size for the study is not based on any statistical hypothesis. The mean differences between pre-procedure and post-procedure measures will be analyzed using paired t-tests. A p-value of ≤ 0.05 will be considered to indicate statistical significance. Descriptive statistics will be generated to describe study findings (i.e. subject demographics, plaque volume, lumen volume, vessel size, etc.).		

1. Key Roles

Version 23JUL2020 Page 7 of 23

Investigator:

[name], PhD, FACC [name] [contact] [contact]

Co-Investigators:

TBD

Center:

NYU Langone Health [name]

2. Introduction

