2.2 Study Description

A single center prospective, randomized study will be conducted to investigate plaque removal and luminal gain using CSI's DIAMONDBACK 360® Peripheral Orbital Atherectomy System (OAS) (St.Paul, MN) versus Medtronic's Hawkone Directional Atherectomy system (DAS) (Minneapolis, MN) assessed by angiography and Intravascular Ultrasound (IVUS) in patients diagnosed with symptomatic obstructive femoro-popliteal disease will be analyzed.

Subjects will be randomized in a 1:1 fashion to receive treatment with either OAS (using CSI device) followed by Inpact Admiral drug coated balloon (DCB) or DAS (using the Hawkone device) followed by DCB. Subjects in both arms will undergo IVUS before and after atherectomy, as well as at the conclusion of the procedure.

Clinical data will be collected at baseline, immediately prior to the procedure, during and immediately after the procedures, and within 30 days, 6 and 12 months office visits after the procedure. Data may also be collected at office or hospital visits which are not scheduled but may occur up to 12 months after the procedure, if they pertain to treatment related to the obstructive femoro-popliteal disease. Data to be collected for this study includes demographics, medical history, procedural parameters and follow-up.

The study will be conducted at one study center, 100 subjects will be enrolled, with 60 subject accrued in the trial: 30 patients randomized to the OAS arm and 30 patients randomized to the

Version 23JUL2020 Page 8 of 23

DAS arm. The duration of the study is expected to be approximately 2 years from the date of first enrollment (1 year for enrollment of 60 subjects and a year for follow-up).

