2.4 Study Objectives and Endpoints

2.4.a. Primary Objective

 To investigate the hard and soft plaque removal with directional and orbital atherectomy by analyzing changes in plaque volume and composition and vessel size using IVUS). Freedom from complications, target vessel patency and target lesion revascularization (TLR) at 6 months and one year will also be evaluated.

2.4.b. Primary Endpoint

Acute luminal gain (increase in minimal luminal area via IVUS measurement immediately following atherectomy)

2.4.c. Secondary Endpoints

- Plaque burden reduction. The plaque composition and amount of removed plaque will be analyzed via IVUS.
- Device success (≤ 30% residual stenosis following atherectomy, as measured by angiography, without adjunctive endovascular interventions)
- Rate of procedural angiographic complications such as dissection, perforation, emboli, abrupt closure, need for bail out stenting.
- Major Adverse Event Rate at 30 days post procedure defined as clinical TLR, major unplanned amputation of the treated limb, or all-cause mortality
- Rate of clinical TLR, unplanned amputation of the treated limb, or all-cause mortality at 6 and 12months post index treatment.
- Primary patency at 1 year defined as freedom from target lesion restenosis detected with duplex ultrasound Peak Systolic Velocity Ratio (PSVR) is ≤ 2.4
- Rate of Hemodynamic Improvement as assessed by changes in ABI at 6 and 12 months as compared to post-procedural baseline (i.e., within 30 days).
- Improvement in Rutherford Clinical Category within 30 days, at 6 months and at 12 months, defined as an improvement in clinical status indicated by a decrease of one or more in Rutherford Clinical Category compared to baseline, that is attributable to the treated limb (in cases of bilateral disease).

Version 23JUL2020 Page 10 of 23

3. Investigator Selection and Responsibilities

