8.2 Statistical and Data Analysis Methods

The Biostatistician from NYULMC will perform the analysis in collaboration with the Principal Investigator. No interim analyses are planned.

Descriptive statistics will be generated to describe study findings (i.e. subject demographics, plaque volume, lumen volume, vessel size, etc.). The mean differences between pre-procedure and post-procedure measures will be analyzed using paired t-tests. The pre- and post-procedure changes in the primary and secondary outcomes will be compared between the two treatment arms by the Intention to treat (ITT) principle. Multivariable linear regressions will be used to compare the change between treatments adjusting for subject demographics and other covariates. A p-value of \leq 0.05 will be considered to indicate statistical significance.

Group sample sizes of 30 and 30 achieve 80% power to detect a difference of 0.7 standard deviation difference in the mean of the primary outcome between the two groups with a significance level 0.05.

IVUS DICOM Image Analysis

Anonymized IVUS Images and selected angiograms should be recorded on DICOM format and archived on DVD for off-line analysis.

Quantitative assessment of the treated segments will be performed using planimetry echoPlague software (Inedc, Mountain View, CA).

9. Data Safety Monitoring

Due to the fact that this is an investigator initiated trial there will be no external monitoring or auditing for this study. In this study, a Clinical Event Committee (CEC) or a Data Safety Monitoring Board (DSMB) will not be used. The Principal Investigator will conduct interim monitoring of any serious adverse event at the time of occurrence and annually to assure the continuing safety of participants, relevance of the study question, appropriateness of the study protocol compliance and integrity of the accumulating data. The PI in conjunction with NYU IRB will be responsible for monitoring the data and conducting safety reviews every12 months when annual re-approval is sought. During the review process, the PI and NYU IRB will evaluate whether the study should continue unchanged, require modification/amendment, or close to enrollment. This study will not have predefined stopping rules due to the fact that both devices are proven to be safe in multiple clinical trials and approved by FDA for routine clinical practice.

Version 23JUL2020 Page 20 of 23

10. Investigator Records and Reports

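### The p ≤ 0.05 rule covers every test in the plan: the primary comparison, about 12 to 14 unpowered secondary comparisons, and pre/post tests that cannot compare the devices

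*Combined protocol and SAP*

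**What the plan says.** Section 8.2 (Statistical and Data Analysis Methods) lists three kinds of test in turn.

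- Pre/post tests: "The mean differences between pre-procedure and post-procedure measures will be analyzed using paired t-tests". It does not say whether these are run per arm or pooled.
- Between-arm tests, by intention to treat: "changes in the primary and secondary outcomes will be compared between the two treatment arms".
- Multivariable regressions that compare the change between treatments, adjusted for demographics and other covariates.

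One threshold then follows for all of them: a p-value of at most "0.05 will be considered to indicate statistical significance".

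The power statement concerns the primary outcome only: "Group sample sizes of 30 and 30 achieve 80% power to detect" a "0.7 standard deviation difference in the mean of the primary outcome" "between the two groups with a significance level 0.05".

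The Statistical Analysis row of the Protocol Summary repeats the threshold. The paired t-test is the only inferential method it names, and it says the sample size rests on no statistical hypothesis. Section 2.3 gives the purpose as evaluating whether directional atherectomy is superior to orbital atherectomy. Section 2.4 names one primary endpoint, acute luminal gain on IVUS, and eight secondary bullets, several with more than one time point. No section gives a testing order, a multiplicity rule, or a statement that secondary or pre/post results are exploratory.

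**The concern.** The trial asks a comparative question, and one comparison was powered to answer it. The significance rule does not separate that comparison from the rest. Two different problems follow.

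1. **Multiplicity.** A chance result on one of about a dozen secondary comparisons may be declared significant on the same footing as the primary result.
2. **Wrong question.** A pre/post p-value may be declared significant although it only shows that the measure changed after treatment. Lesions enter with at least 70% stenosis (section 4.3) and are then debulked, so lumen gain is expected with either device. The synopsis, read alone, makes this the trial's only test.

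The first is a matter of type I error. The second is not: such a result may well be a true positive, but it does not bear on superiority.

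**Working it through.** **The plan's own figure.** Two-sample comparison, 30 per arm, difference 0.7 SD, α = 0.05 (two-sided assumed, since the plan does not say). Normal approximation: Φ(0.7 × √(30/2) − 1.96) = Φ(0.751) = 77.4%. The noncentral t gives 76.0%; one-sided tests give about 85%. The stated 80% is not reproduced at exactly 0.7 SD. It corresponds to 0.72 SD (normal) or 0.74 SD (t), so 0.7 may be rounded. What matters here is that this is the only power statement, and it covers the primary outcome alone.

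**Count of secondary between-arm comparisons (section 2.4.c).**

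| Secondary endpoint | Strict count | If split further |
|---|---|---|
| Plaque burden; composition; amount removed | 1 | up to 3 |
| Device success | 1 | 1 |
| Angiographic complications | 1 | up to 5 |
| Major adverse events, 30 days | 1 | 1 |
| TLR, amputation or death, 6 and 12 months | 2 | 2 |
| Primary patency, 1 year | 1 | 1 |
| ABI, 6 and 12 months | 2 | 2 |
| Rutherford category, 3 visits | 3 | 3 |
| **Total** | **12** | **14 with plaque split; 18 with complications also split** |

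Section 8.2 speaks of comparing changes. Read literally, that leaves 6: plaque burden, ABI twice and Rutherford three times.

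**Chance of at least one p ≤ 0.05 when no secondary difference exists.** For k independent tests this is 1 − 0.95^k. For pairwise correlation ρ it is 1 − ∫ [Φ((1.96 − √ρ·u)/√(1 − ρ)) − Φ((−1.96 − √ρ·u)/√(1 − ρ))]^k φ(u) du. The documents give no correlations, so ρ is an assumption.

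| k | Independent | ρ = 0.3 | ρ = 0.5 | ρ = 0.7 |
|---|---|---|---|---|
| 6 | 26.5% | 24% | 21% | 16% |
| 12 | 46.0% | 40% | 32% | 23% |
| 13 | 48.7% | 42% | 33% | 24% |
| 14 | 51.2% | 44% | 35% | 25% |
| 18 | 60.3% | 51% | 40% | 28% |

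**Sparse binary outcomes.** With 30 per arm, Fisher's exact test has a true size well below 5%: 0.9% at a 10% event rate, 1.7% at 15%, 2.2% at 20%, 2.6% at 30%, and practically zero at 2%. Take 13 independent tests: four at full 5% size, and nine binary with assumed rates of 30% (device failure), 15% (complications), 2% (30-day events), 10% and 15% (later composites), 20% (patency loss) and 20% (Rutherford, three times). The chance is then 1 − 0.95⁴ × 0.9739 × 0.9828 × 1.0000 × 0.9906 × 0.9828 × 0.9778⁴ = 31%. With chi-square tests and the same rates it is 46%. The plan names no test for binary outcomes.

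**Paired pre/post test.** Noncentral t, n − 1 degrees of freedom, noncentrality d√n, two-sided 5%. The documents give no standardised change d, so d is assumed.

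| d | n = 30 (per arm) | n = 60 (pooled) |
|---|---|---|
| 0.5 | 75.4% | 96.8% |
| 0.8 | 98.8% | over 99.9% |
| 1.0 | 99.96% | over 99.9% |

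If the gain is large, both arms are expected to be significant. If it is moderate and the same in both arms (d = 0.5, tested per arm), exactly one arm is significant with probability 2 × 0.754 × 0.246 = 37%, although the devices do not differ. Pooling removes the device contrast altogether.

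**The case against.** The best defence is that the primary inference is already protected. There is one primary endpoint, the power statement is tied to it, no interim analysis is planned, and section 8.2 specifies a between-arm intention-to-treat comparison. This stands: secondary tests do not raise the error rate of the primary test. The paired tests are the only named inference in the synopsis, not in the full plan.

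The defence also limits the size of the problem, and most of this stands.

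- A reader might infer that a false secondary finding is more likely than not. On 12 or 13 comparisons no scenario above reaches one half. It takes 14 independent tests to pass it, and repeated ABI and Rutherford measures and overlapping event composites are unlikely to be independent.
- A reader might take 13 as the minimum number of comparisons. The strict count is 12, and 6 on a literal reading of 8.2.
- A reader might call a positive pre/post result near-certain for every measure in each arm. That depends on an effect size the documents do not give, and on per-arm testing they do not specify.
- A reader might infer that non-significant safety comparisons will be reported as equivalence. No section proposes this. It is true that 0 events in 30 would leave an exact 95% upper limit of 1 − 0.025^(1/30) = 11.6%, but that is a caution for reporting, not a fault in the text.

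What the defence does not supply is any sentence that separates the confirmatory test from the rest.

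**Conclusion.** The point holds as a gap in the significance rule. Followed as written, the plan lets an unpowered secondary result, or a pre/post result that does not compare the devices, be declared significant in a trial whose purpose is device superiority.

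The chance of at least one false significant secondary result is roughly 23% to 51% for 12 to 14 comparisons. It assumes no true secondary difference, full 5% test size, and correlations from 0.7 down to 0. With 6 comparisons it is 16% to 26%, and Fisher's exact test on sparse outcomes lowers it further (31% instead of 49% for 13 independent tests at the assumed event rates). All these figures are well above 5%.

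The pre/post part rests on logic rather than on the assumed effect sizes: whatever its power, a paired test does not estimate the difference between devices. The documents do not support the stronger inference that the primary result is compromised by the secondary tests. Section 8.2 does leave open whether the unadjusted or the adjusted analysis decides the primary comparison, which is a separate matter that the same edit can settle.

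**What to change.** Edit section 8.2 and the Statistical Analysis row of the synopsis.

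1. Limit the p ≤ 0.05 rule to one confirmatory test, the between-arm intention-to-treat difference in acute luminal gain. Say whether the unadjusted or the regression-adjusted analysis is that test.
2. State this comparison in the synopsis, and reconcile the synopsis remark on sample size with the power statement in 8.2.
3. Report secondary between-arm results as estimates with 95% confidence intervals, labelled exploratory.
4. Label pre/post results as descriptive, and say whether they are per arm or pooled. The tests need not be removed.

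The cost is wording only, with no added subjects, visits or measurements. The downside is that no formal claim can be made from a secondary endpoint, but the plan powers none of them. If a formal secondary claim is wanted, a prespecified order or an adjusted threshold is needed instead; Bonferroni over 13 tests would be 0.05/13 = 0.0038 each.

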While both directional and orbital atherectomy systems have demonstrated improved outcomes versus balloon angioplasty alone, no studies have been performed to directly compare whether one form of atherectomy is superior to the other. With the increased incidence of significant PAD and the increased need for atherectomy in order to achieve successful percutaneous intervention, it would be extremely beneficial to know whether one type of atherectomy system is preferred over another. There are several theoretical advantages of DAS over OAS: DAS allows for possibly larger amount of plaque removal (de-bulking) which leads to a larger luminal gain and vessel diameter that in turn may lead to a better long term vessel patency rates and lower rates of target vessel revascularization. The purpose of this study will be to evaluate whether directional atherectomy is superior to orbital atherectomy in treating long femoro-popliteal lesions.

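### The stated 80% power at 0.7 SD with 30 per arm is 76% for a two-sided two-sample t-test (80% needs 0.74 SD), and the synopsis gives a different account of the sample size

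*Combined protocol and SAP*

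**What the plan says.** Section 8.2 (Statistical and Data Analysis Methods) contains the only power statement: "Group sample sizes of 30 and 30 achieve 80% power to detect a difference of 0.7 standard deviation difference" in the mean primary outcome between arms, at significance level 0.05. It gives no raw difference, no SD, no named test and no sidedness.

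For the between-arm analysis, the same section says: "Multivariable linear regressions will be used to compare the change between treatments adjusting for subject demographics and other covariates". The covariates are not listed, and nothing is said about how much outcome variance they should explain.

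The Statistical Analysis row of the Protocol Summary says something else about the same 60 patients: "The sample size for the study is not based on any statistical hypothesis". That row names only paired pre/post t-tests. It mentions neither a between-arm test nor a detectable difference.

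Section 2.3 frames the trial as a between-arm superiority question: "The purpose of this study will be to evaluate whether directional atherectomy is superior to orbital atherectomy".

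**The concern.** The power sentence supplies n, effect size, alpha and power, so it can be checked directly. It does not come out at 80% under an ordinary two-sample comparison, one-sided or two-sided. A reader also meets two accounts of where 60 came from: one that rests on no hypothesis, and one that gives a power for a between-arm difference.

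This sentence is the only place the documents say what 60 patients can show on the superiority question, and a non-significant result would be read against it. Without any gain from covariates, the type II error at a true difference of 0.7 SD is 24%, not the implied 20%. A reader of the synopsis alone learns of no between-arm comparison and no detectable difference.

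**Working it through.** **Inputs.** From section 8.2: n = 30 per arm, standardised difference d = 0.7, alpha = 0.05, stated power 80%. From section 2.2: 1:1 allocation. From section 2.4.b: a continuous primary outcome, the IVUS increase in minimal luminal area after atherectomy. Test and sidedness are not stated, so each standard reading is tried.

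**Step 1: try to reproduce 80% at d = 0.7, unadjusted.** For two equal arms the noncentrality is d × √(n/2) = 0.7 × √15 = 2.711, with 30 + 30 − 2 = 58 degrees of freedom. Power is the probability that a noncentral t variable with these parameters exceeds the critical value (for a two-sided test, either critical value).

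| Reading | Critical value | Power at 0.7 SD |
|---|---|---|
| Two-sided t-test | 2.002 | 76.0% |
| Two-sided normal approximation: Φ(2.711 − 1.960) | 1.960 | 77.4% |
| One-sided t-test | 1.672 | 85.0% |

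None gives 80%. The two-sided readings fall short and the one-sided reading overshoots.

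**Step 2: what 30 per arm does deliver at 80%.** Solving the two-sided t-test power for d gives 0.736 SD. The normal approximation gives (1.960 + 0.842)/√15 = 0.723 SD. As a check, two-sided t-test power at d = 0.74 is 80.5%. Going the other way, d = 0.7 needs 33 per arm for 79.97% or 34 per arm for 81.2%.

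**Step 3: the adjusted regression.** If covariates explain a share R² of outcome variance, the residual SD shrinks by √(1 − R²). With k covariates the noncentrality becomes 0.7/√(1 − R²) × √15 on 58 − k degrees of freedom. R² and k are not in the documents, so both are assumptions shown over a range.

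| Assumed R² | Noncentrality | Power at 0.7 SD, k = 8 to k = 1 |
|---|---|---|
| 0 | 2.711 | 75.8% to 76.0% |
| 0.05 | 2.782 | 77.9% to 78.1% |
| 0.10 | 2.858 | 80.0% to 80.2% |
| 0.20 | 3.031 | 84.4% to 84.6% |

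The R² needed for exactly 80% is 0.095 with one covariate and 0.099 with eight.

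**Step 4: the two accounts side by side.** The Protocol Summary denies any hypothesis basis for the sample size. Section 8.2 attaches a power, an alpha and an effect size for a between-arm difference to the same 30 and 30. Both carry the same version date (23JUL2020), so neither supersedes the other. Nothing in either place says whether 60 was chosen for feasibility and the power then described, or whether 60 came from the calculation.

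**The case against.** The strongest reply on the arithmetic is rounding. The effect size is given to one decimal, and both 0.736 (t-test) and 0.723 (normal approximation) round to 0.7. The sentence would then be an ordinary detectable-difference statement with a decimal dropped. This is plausible and may be what happened. It does not make the printed pair correct: rounding the difference down while keeping 80% overstates sensitivity, and the documents do not signal any rounding.

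The second reply is that the t-test is the wrong benchmark, because the planned between-arm comparison is adjusted regression and a multiple correlation of about 0.31 (R² about 0.10) restores 80% at exactly 0.70 SD. This also stands as a possibility. But section 8.2 neither names the covariates nor states an R², so 80% cannot be verified by that route.

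Third, the two sample-size statements can be read together: a number chosen for feasibility, followed by a description of the power it gives. The verb in section 8.2 allows that reading, so this is an unreconciled presentation and not necessarily a logical contradiction. The reader still has to supply the reconciliation.

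Finally, the effect is small and no decision rule in the protocol turns on it. That is conceded, and it is why only a wording change is asked for.

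**Conclusion.** The concern holds. At exactly 0.7 SD, 30 per arm gives 76.0% power on a two-sided unadjusted t-test at alpha 0.05, which is 4.0 points below the stated 80%. The difference detectable at 80% is 0.736 SD, which is 0.036 SD above the stated 0.7. These figures assume all 60 patients are evaluable. The stated 80% becomes right only if 0.7 is a rounded 0.74, or if covariates explain about 10% of outcome variance; the documents state neither. The synopsis and section 8.2 also give unreconciled accounts of the sample size. The size is modest: this is a reporting correction that should be made, with no bearing on enrolment, endpoint or conduct.

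**What to change.** In section 8.2, replace the power sentence with, for example: 30 and 30 evaluable subjects give 76% power to detect a between-arm difference of 0.7 SD in the primary outcome, or 80% power to detect 0.74 SD (unadjusted two-sample t-test, two-sided alpha 0.05); covariate adjustment may increase this.

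If 80% at 0.7 SD was meant for the adjusted regression, say so instead: name the covariates and state the assumed R² (about 0.10 is needed) with its source.

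Then align the Statistical Analysis row of the Protocol Summary with section 8.2. If 60 was chosen on feasibility grounds, say so in both places and present the power as descriptive. If it came from the power calculation, remove the sentence denying a hypothesis basis. Give the same detectable difference in both places.

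The cost is wording in two places. Enrolment, endpoint and analysis stay as they are, and the only loss is a slightly less favourable stated sensitivity unless an R² can be justified.
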